1.6.2. Potential Benefit

A Marketing Authorisation Application was approved in EU/EEA on 16 December 2014 for the indication “LYNPARZA monotherapy for the maintenance treatment of adult patients with platinum-sensitive relapsed *BRCA*-mutated (germline and/or somatic) high grade serous epithelial ovarian, fallopian tube, or primary peritoneal cancer who are in response (complete response or partial response) to platinum-based chemotherapy”.

A New Drug Application was approved in the US on 19 December 2014 for the indication “LYNPARZA monotherapy in patients with deleterious or suspected deleterious germline *BRCA* mutated (as detected by an FDA-approved test) advanced ovarian cancer who have been treated with three or more prior lines of chemotherapy”. The tablet formulation of olaparib was approved in August 2017 US for the maintenance treatment of adult patients with recurrent epithelial ovarian, fallopian tube or primary peritoneal cancer, who are in a complete or partial response to platinum-based chemotherapy; and for the treatment of adult patients with deleterious or suspected deleterious germline breast cancer susceptibility gene (*BRCA*)-mutated (gBRCAm) advanced ovarian cancer who have been treated with 3 or more prior lines of chemotherapy.

Phase II clinical studies have investigated the effect of olaparib either as monotherapy or in combination with other chemotherapy agents in cancer patients. In patients carrying

germline *BRCA* mutations, monotherapy studies in patients with heavily pre-treated breast cancer have reported an ORR of up to 41%, A phase 3 trial, OlympiAD showed that olaparib provided a significant benefit over standard therapy; median PFS was 2.8 months longer and the risk of disease progression or death was 42% lower with olaparib monotherapy than with standard therapy.

US approved in January 2018 the tablet formulation for patients with deleterious or suspected deleterious gBRCAm, HER2-negative MBC who have previously been treated with chemotherapy in the neoadjuvant, adjuvant or metastatic setting. Patients with hormone receptor (HR)-positive breast cancer should have been treated with a prior endocrine therapy or be considered inappropriate for endocrine treatment. Based on these results and data from the full clinical program to date, it is anticipated that olaparib will have a positive benefit risk profile for the treatment of the small well-defined population of advanced triple negative breast cancer patients with promoter methylation of *BRCA*.

2. Objectives

2.1. Primary Objective

- To analyse the olaparib efficacy in the treatment of patients diagnosed of advanced triple negative breast cancer (TNBC) with *BRCA1* and/or *BRCA2* promoter methylation assessed in somatic DNA.

2.2. Primary End-point

- Objective Response Rate (ORR) defined as Complete Response (CR) plus Partial Response (PR) according to Response Evaluation Criteria in Solid Tumours (RECIST) version 1.1.

2.3. Secondary Objectives

- To analyse other efficacy measures.
- To analyse olaparib safety.
- To explore changes in the methylation status of *BRCA1/2* promoter in germline DNA prior and after treatment discontinuation for any reason and correlate germline *BRCA1/2* methylation data with efficacy parameters.
- To correlate *BRCA1/2* methylation between germline and somatic DNA and between primary tumour and metastatic lesions.
- To correlate *BRCA1/2* expression with methylation status of *BRCA1/2* promoter and efficacy parameters.

2.4. Secondary End-points

- Clinical Benefit Rate (CBR), Response Duration (RD), Progression Free Survival (PFS) and Overall Survival (OS).
- Adverse events defined by the NCI-CTCAE (National Cancer Institute Common Terminology Criteria for Adverse Events) version 4.0.
- The methylation status of *BRCA 1* and *2* promoters will be measured in germline DNA from blood cells at the beginning of the study and after disease progression, or at the end of study treatment by other reason, and in paired primary and metastatic lesions. It will be analysed: 1) changes of germline methylation pre and post-treatment; 2) correlation between germline methylation status and efficacy outcome data; 3) correlation between germline and somatic methylation status and 4) correlation between primary and metastatic lesions.

- mRNA levels of *BRCA1* and 2 will be assessed in blood and available tumour samples. Expression data will be correlated with promoter methylation status of *BRCA* and outcome data.

2.5. Exploratory Objectives

- To explore biomarkers of clinical activity in tumour and blood samples.

2.6. Exploratory End-points

[figure not shown]
- Biomarker values from the primary or metastatic tumour tissue could be used for assessment of biomarkers related to breast tumour sensitivity and/or resistance to olaparib (e.g. may include but not limited to somatic *BRCA1/2* mutational status or other genes related to cancer susceptibility or thought to be related to the drug mechanism of action). These samples will be instrumental to explore biomarkers of response or resistance to olaparib.
- DNA and RNA obtained from the blood samples collected during the study may be used for potential pharmacogenomics analyses related to drug response or adverse drug reactions (including but not limited to comparison of germline DNA or RNA patterns of patients who respond well and those who respond poorly to treatment). For example, genes coding drug metabolizing enzymes, drug transport proteins or genes involved in DNA repair pathways, cancer susceptibility or thought to be related to the drug mechanisms of action may be analysed.
- Specific mutations or epigenetic biomarkers identified in pre-therapy tumour specimens as potentially linked to treatment response could be tested in plasma DNA. A targeted NGS panel may be designed to study all the candidate mutations. Plasma DNA has also the potential to be a surrogate of tumour load and may also be instrumental to monitor disease.

3. Investigational Plan

3.1. Study Design

This is a multicenter, non-randomized, phase II clinical trial to assess the efficacy and safety of olaparib in monotherapy in patients diagnosed of advanced triple negative BC with methylation of *BRCA1* and/or 2 promoters (assessed in DNA from metastatic lesions) and absence of *BRCA1* and 2 germline mutations. Patients must have received at least one previous regimen in the advance disease setting.

Figure 1 Study Design

Potential eligible patients will be screened to assess germinal (g) *BRCA* mutational status at Myriad laboratory (unless the *BRCA* mutational status is already known based on a Myriad previous report).

Blood samples for mutational *BRCA* screening could be sent either 1) during the previous line of treatment, once the eligibility criteria have been reviewed and the patient is considered a potential candidate for the study (at least the patient must have measurable and biopsiable disease) or 2) after end of the line of treatment prior to study enrolment (simultaneously to the shipment of the tumour samples for methylation analysis). A specific ICF must be signed for this screening assessment.

Somatic (s) *BRCA* promoter methylation will be assessed also centrally at an external reference central laboratory selected by GEICAM. Tumour samples must proceed from a metastatic lesion, it is strongly recommended to obtain it after the line treatment immediately previous to the study entry.

Patients with a positive methylation status on *BRCA1* and/or *BRCA2* and lacking of known deleterious or suspected deleterious mutations in both genes could be included in the study to receive olaparib tablet formulation at 600 mg daily dose (given in two oral administrations of 300 mg every 12 hours approximately). Blood and tumour samples collected from all registered patients could be used for the secondary and exploratory analysis of the study, including but not limited to the assessment of germline methylation status and gene expression levels of *BRCA1/2*.

Patients will continue to receive their treatment until objective disease progression, symptomatic deterioration, unacceptable toxicity, death or withdrawal of consent, whichever occurs first.

Each assessment of tumour response will be performed as scheduled according to the calendar regardless of any dosing delay to prevent the introduction of bias into the assessment of efficacy.

According to RECIST v.1.1 in case of patients with a global deterioration of health status requiring discontinuation of treatment without objective evidence of disease progression at that time every effort should be made to document objective progression, even after discontinuation of treatment. The objective response status of such patients should be determined considering RECIST v.1.1 instructions. In case any efficacy assessment cannot be done, they will be considered not evaluable for response rate analysis and PFS will be censored at the date of the last tumour assessment.

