8.2.1. Patient Populations

Intent to treat population (ITT): The ITT population will include all patients who are enrolled in the study.

Efficacy population: a subset of the ITT population that have received at least one dose of study medication and has performed at least one tumour response assessment according to RECIST v.1.1 (unless a progression, death or unacceptable toxicity is seen before the first tumour response assessment) and without major protocol deviations according to the protocol deviation manual.

The **efficacy** population will be the primary population for the efficacy analysis.

It will be performed a sensitivity analysis using the ITT population.

Safety population: will include all patients enrolled in the study who received at least one dose of treatment. This population is for the safety analysis.

Population for Biomarker Analysis: a subset of enrolled patients with evaluable blood and/or tumour samples required for achievement of the secondary and exploratory objectives of the study.

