8.2.6.1. Analyses of Primary Endpoint

The primary endpoint is ORR

Objective Response Rate (ORR): A patient will be considered to have achieved an OR if the patient has a sustained complete response (CR) or partial response (PR) according to RECIST v.1.1 definitions. Otherwise, the patient will be considered as non-responders in the ORR analysis. ORR will be estimated by dividing the number of patients with objective response (CR or PR) by the Efficacy population ("response rate").

$$\text{Objective Response Rate} = \frac{\text{Number of CRs + PRs}}{\text{Efficacy population}}$$

The ORR will be reported, including a 95% confidence interval.

These analyses will be conducted at a two-sided 0.05 level of significance.

The number of responders needed at the end of stage 2 to reject the null hypothesis is at least 14 responders.

Additional sensitivity analyses will be outlined in the SAP. For the analysis in the ITT population, patients with inadequate data for tumour assessment (e.g., no baseline assessment or no follow-up assessments) will be considered as non-responders in the OR rate analysis.

In addition, the best objective response for each patient will be summarized.

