### **4.2 Efficacy population**

A subset of the ITT population that have received at least one dose of study medication and has performed at least one tumour response assessment according to RECIST version 1.1 (unless PD, death or unacceptable toxicity is observed before the first tumour response assessment) and without major protocol deviations according to the protocol deviation manual.

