### 9.2.1.1 Analyses of Primary Endpoint

The primary endpoint is ORR.

**Objective Response Rate (ORR):** A patient will be considered to have achieved an objective response (OR) if the patient has a complete response (CR) or partial response (PR) according to RECIST version 1.1 (4) definitions. Otherwise, the patient will be considered as non-responder in the ORR analysis. ORR will be estimated by dividing the number of patients with objective response (CR or PR) by the **Efficacy** population ("response rate").

$$\text{Objective Response Rate} = \frac{\text{Number of CRs + PRs}}{\text{Efficacy Population}}$$

The ORR will be reported, including a 95% confidence interval using the Clopper-Pearson method (5).

These analyses will be conducted at a two-sided 0.05 level of significance.

The number of responders needed at the end of stage 2 to reject the null hypothesis is at least 14 responders.

Additional sensitivity analyses will be done with the ITT population. For the analysis in the ITT population, patients with inadequate data for tumour assessment (e.g., no baseline assessment or no follow up assessments) will be considered as non-responders in the ORR analysis.

In addition, the best objective response (BOR) for each patient will be summarized.

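### Patients who deteriorate and cannot be assessed are called 'not evaluable' in one place and non-responders in another, and only the protocol puts an 80% dose condition on the step 1 twelve

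*Protocol*

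**What the plan says.** **Design text.** Protocol 3.1 and SAP 3 describe patients whose general health declines so far that treatment stops without objective progression. Where assessment is impossible, the rule is: "they will be considered not evaluable for response rate analysis and PFS will be censored at the date of the last tumour assessment". Protocol 6.1 repeats the rule for the applicable efficacy endpoints, but its condition reads 'can be done' where the other two read 'cannot be done'.

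**ORR rules.** Both documents divide by the Efficacy population. For a patient without CR or PR, Protocol 8.2.6.1 says "Otherwise, the patient will be considered as non-responders in the ORR analysis" and SAP 9.2.1.1 says "Otherwise, the patient will be considered as non-responder in the ORR analysis". For ITT, the protocol says "patients with inadequate data for tumour assessment (e.g., no baseline assessment or no follow-up assessments) will be considered as non-responders", and the SAP says the same.

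**Efficacy population.** At least one dose, at least one tumour assessment and no major deviation are required. The assessment is waived "unless a progression, death or unacceptable toxicity is seen before the first tumour response assessment" (Protocol 8.2.1, Patient Populations) or "unless PD, death or unacceptable toxicity is observed before the first tumour response assessment" (SAP 4.2).

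**PFS.** Protocol 8.2.6.2 and SAP 9.2.1.2 censor at the last assessment only patients who have neither progressed nor died, or who start a new anti-cancer therapy first.

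**Step 1.** Recruitment continues if at least 4 of the first 12 evaluable patients respond (Protocol 8.2.10, SAP 8). Protocol 8.2.5 adds that these twelve must have received at least 80% of the planned dose. SAP 5.4 sets no minimum compliance for efficacy analyses and uses 80% of the planned number of doses only to define a compliant patient. SAP 8 has no dose condition.

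**The concern.** One patient can be given two statuses for the primary endpoint, depending on which section the analyst follows. Patients who stop because they are deteriorating are unlikely to be responders, so setting them aside would tend to raise the reported ORR.

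The exposure is greatest at step 1, which is the trial's only stopping rule. It counts responders among evaluable patients, and the only text that says who is not evaluable for response is the deterioration text. The protocol's dose condition then selects patients on something that happens after enrolment. The protocol's own dose-modification table allows a second reduction to 200 mg from 300 mg twice daily, which is 200/300 = 67% of the starting dose. A patient treated exactly as the protocol allows could therefore fall below 80%, depending on whether 'planned dose' means the starting or the adjusted dose, and the protocol does not say which. Selecting on dose received can bias the decision, and two analysts working from the two documents could review different sets of twelve.

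**Working it through.** **1. The passages set against each other.**

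| Patient who deteriorates and cannot be assessed | Design text | ORR sections |
|---|---|---|
| ITT, no follow-up scan | not evaluable | non-responder |
| Efficacy population, died before first scan | not evaluable | non-responder |
| Efficacy population, earlier scan without response, later scan impossible | not evaluable, if 'any assessment' means any one missing assessment | non-responder |
| No scan and no progression, death or unacceptable toxicity before it | not evaluable | outside the Efficacy population under SAP 4.2: no conflict in the primary analysis |

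The first three rows are contradictions; the fourth is not. The PFS clause also conflicts: taken literally, it censors a patient who deteriorates and then dies, whereas the PFS sections count her death as an event.

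**2. The plan's own design.** Inputs from Protocol 8.1.1: null 30%, alternative 54%, 12 then 31 evaluable, continue at 4 or more, reject at 14 or more. With b(12, x, p) the binomial probability,

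P(reject) = Σ (x = 4 to 12) b(12, x, p) × P(Bin(19, p) ≥ 14 − x).

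At p = 0.30 the chance of passing step 1 is 0.5075 and P(reject) is 0.0503. At p = 0.54, P(reject) is 0.861. A search for the optimal Simon design at 0.05 and 80% returns the same 12, 31 and 14, but continues at 5 or more (0.0428 and 0.807). That boundary is a separate matter; the written boundary of 4 is used below.

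**3. A rate for the affected group.** The documents give none. The nearest figure is the 'Not evaluable' row of Protocol Table 3 for the olaparib breast cohorts: (0 + 0 + 1 + 2)/(27 + 27 + 26 + 62) = 3/142 = 2.1%, from all causes. Rates of 5% and 10% are assumptions.

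**4. Effect if a fraction f is dropped, all of them non-responders.** If the 30% null applies to all treated patients, the rate among those left is q = 0.30/(1 − f); for f = 3/142, q = 0.3065. The chance of passing step 1 is P(Bin(12, q) ≥ 4). The false-positive rate comes from an exact recursion over enrolled patients. It is shown for enrolment to 31 evaluable with at most 34 enrolled (Protocol 8.1.1), and for 34 enrolled outright (Protocol 3.1.1 and 8.2.10, SAP 8).

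| f | q | Pass step 1 | False positive, stop at 31 | False positive, 34 enrolled |
|---|---|---|---|---|
| 0 | 0.3000 | 50.7% | 0.050 | 0.098 |
| 2.1% | 0.3065 | 52.7% | 0.059 | 0.100 |
| 5% (assumed) | 0.3158 | 55.6% | 0.072 | 0.101 |
| 10% (assumed) | 0.3333 | 60.7% | 0.091 | 0.104 |

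If 30% refers to assessable patients only, q stays at 0.30. For f = 2.1%, 5% and 10% the false-positive rates are then 0.050, 0.049 and 0.041 (stop at 31), or 0.086, 0.071 and 0.048 (34 enrolled). None exceeds its f = 0 value.

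**5. How often, and effect on the estimate.** At 2.1%, 34 × 0.0211 = 0.7 patients are expected. The chance of at least one among the first 12 enrolled is 1 − (1 − 0.0211)^12 = 23%. Dropping one patient moves 14/34 = 41.2% to 14/33 = 42.4%, and the Clopper-Pearson lower limit from 24.6% to 25.5%.

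The documents give nothing from which to size the 80% dose condition.

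**The case against.** 'Not evaluable' need not mean removed from the denominator. Table 3 keeps its not-evaluable patients in: 8/62 = 12.9% includes two of them. On that view the ORR sections, being the specific rule, govern and the design text is only descriptive. This is a sensible reading, but nothing in either document gives the ORR sections precedence, and it does not settle who is evaluable at step 1.

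The group is also small. Note r of the Study Schedule continues scans every 8 weeks after treatment stops if progression is unconfirmed and no new therapy has begun. Entry requires ECOG 0–1 and a life expectancy of at least 16 weeks, twice the interval to the first scan. This stands, and it limits the size.

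On the 80% condition, SAP 5.4 may be a deliberate replacement: it drops the word 'final' that the protocol attaches to the efficacy analysis, and the SAP is allowed to modify the protocol. It does not say that it does so here, and the protocol sentence remains in force.

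A reader might infer more than the documents support:

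- **That the Efficacy population contradicts the design text for patients with no scan and no qualifying event.** Under SAP 4.2 the two agree. Counting these patients as failures is a choice of population, not a correction.
- **That the false-positive rate roughly doubles.** That needs an assumed 10% rate, every such patient dropped, a null for all treated patients, and enrolment stopped at 31 evaluable.
- **That the 0.098 arises here.** It comes from applying the 14-responder rule to 34 patients instead of 31, which is a different issue.

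**Conclusion.** The contradiction is in the current text of both documents and concerns the primary endpoint. The 80% condition is in the protocol only, and 'first 12 evaluable' is undefined, so the two documents can select different patients for the go/stop decision. This should be fixed, but the expected effect is modest: about 2 percentage points on passing step 1, and 0.009 or 0.002 on the false-positive rate, at the 2.1% anchor.

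Those figures assume that every affected patient is dropped and is a non-responder, and that the 30% null describes all treated patients. The anchor covers all causes of non-evaluability, so it may be too high for this group. The pre-specified ITT analysis would expose the effect on the final ORR, provided the design text is not applied there too; it gives no help at step 1. Confidence is medium, because the intended meaning of 'not evaluable' cannot be established from the documents.

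**What to change.** 1. In Protocol 3.1, Protocol 6.1 and SAP 3, replace the final sentence. State that such a patient, if she belongs to the population being analysed (Efficacy or ITT), is a non-responder for ORR and without clinical benefit for CBR unless the available assessments show otherwise. State that PFS follows Protocol 8.2.6.2 and SAP 9.2.1.2, with death as an event. This also removes the 'can be done' slip.
2. In Protocol 3.1.1 and 8.2.10 and SAP 8, define the first 12 evaluable patients as the first 12 members of the Efficacy population in order of enrolment.
3. Remove the 80% condition on the step 1 set from Protocol 8.2.5, in line with SAP 5.4, and report compliance descriptively.

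The sponsor should also reconcile whether symptomatic deterioration before the first scan counts as a progression for the Efficacy population. The protocol waiver says 'a progression' and the SAP says PD. Protocol 3.2 speaks of symptomatic progression, while Protocol 3.1 lists deterioration separately ("until objective disease progression, symptomatic deterioration, unacceptable toxicity, death or withdrawal of consent"). Adding it is the conservative option, but the fix does not depend on it.

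**Cost.** Wording only, with no extra patients or visits; ORR may read slightly lower. The optional addition costs power if 54% is the rate among assessable patients. If all such patients are counted as failures and enrolment stops at 31, power falls from 86.1% to 83.2% at a 2.1% rate, and to 78.6% or 69.1% at the assumed 5% or 10%. If they stay excluded, the corresponding figures are 86.1%, 85.6% and 82.2%.
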